4.4 Study Population

4.4.1 Subject Disposition

Subject disposition will be summarized for screened subjects by enrollment group and overall as the number and percentage of subjects in the following categories:

- Screened (identified as subjects with non-missing informed consent date and enrollment group)
- Did not enroll in the LTT period (identified as screened subjects with missing IWRS enrollment date)
 - Did not enter the OP (identified as a subset with missing OP start date)
 - Reasons for discontinuation, including not reported*
 - Entered the OP (identified as a subset with non-missing OP start date)
 - Reasons for discontinuation, including not reported*
- Enrolled in the LTT period (identified as screened subjects with non-missing IWRS enrollment date)
 - Not treated (identified as enrolled subjects with missing study drug dose start date)
 - Reasons for discontinuation, including not reported*
 - Treated (identified as enrolled subjects with non-missing study drug dose start date)
 - Ongoing (identified as treated subjects with missing study drug last dose date)
 - Completed* (identified as treated subjects with non-missing study drug last dose date who completed)
 - Discontinued* (identified as treated subjects with non-missing study drug last dose date who discontinued)
 - Reason for discontinuation, including not reported*

The categories marked in with “*” will be based on the Study Exit Status CRF.

Subject disposition will be also be summarized for treated subjects by all subgroups of interest defined in Section 4.2.6.

Participation in previous Studies BHV3000-301/302/303 will be summarized by enrollment group and overall for the following populations: screened; enrolled; treated. The number and percentage of subjects in each previous study (total; 301; 302; 303) and treatment group (rimegepant, placebo) will be presented for each population. Note that subjects may participate in multiple studies and be in both treatment groups.

A by-subject listing of subject disposition information, including the reason for discontinuation and previous study participation, will be presented based on the Study Exit Status CRF for screened subjects.

A by-subject listing of eligibility with inclusion and exclusion criteria will be provided for all screened subjects, not just those who have non-missing criteria.

4.4.2 Protocol Deviations

A protocol deviation is any variance from the approved protocol, either intentional or unintentional. The possible categories for all protocol deviation are as follows:

- Informed Consent
- Inclusion/Exclusion Criteria (specify #)
- Concomitant Medication
- SAE Reporting
- Regulatory
- Drug Storage/Preparation
- Drug Administration
- Visit Schedule
- EPro Diary Noncompliance
- Noncompliance (i.e., trends, missed assessments).

A significant protocol deviation is any deviation that could impact subject safety or the integrity of the trial. For the purposes of this study, significant protocol deviations will be defined as the following:

- Inadequate informed consent or initiation of study procedures prior to completing the informed consent
- Subjects receiving an enrollment date in IWRS, but not meeting the inclusion/exclusion criteria
- Unreported SAEs
- Use of prohibited medication as defined by the protocol
- eDiary non-compliance
- Repeated deviations of the same nature for a given site or subject

The sponsor or designee will be responsible for producing the final significant protocol deviation file (formatted as a Microsoft Excel file). This file will include site, subject ID, deviation date, deviation type, and a description of the protocol deviation.

The number and percentage of treated subjects with significant protocol deviations will be summarized by deviation type and by enrollment group and overall. Deviation types will be presented in descending order of overall frequency.

A by-subject listing of significant protocol deviations will be provided for screened subjects.

4.5 Pre-Treatment Characteristics

The following pre-treatment characteristics will be summarized descriptively by enrollment group and overall for treated subjects:

- Demographics and baseline characteristics*#: age (years), continuous and categorical in the subgroups specified in Section 4.2.6; sex; race; ethnicity; height (cm); weight (kg); body mass index (BMI; kg/m²), continuous and categorical in the subgroups specified in Section 4.2.6.
- Medical history by system organ class (SOC) and preferred term (PT)
- Migraine history#: age (years) at migraine onset; time since last migraine (days); number of moderate to severe migraines per month; average duration of untreated migraine attacks (hours); primary migraine type (migraine without aura, migraine with aura); history of migraine without aura; migraine symptoms (e.g., headache attacks lasting 4-72 hours, unilateral location); history of migraine with aura; aura symptoms (e.g., visual, sensory); migraine with aura type (migraine with typical aura, typical aura with headache, typical aura without headache)
- Cardiac and other risk factors*: ischemic coronary artery disease (e.g., angina pectoris, myocardial infarction); other significant underlying cardiovascular disease, etc.
- Prior triptan response by historically discontinued triptan, route (e.g., intravenous, nasal), and reason for discontinuation (e.g., took too long to relieve headache pain) subcategorized as most or all of the time, some of the time, rarely, or never
- Current triptan response by currently used triptan, route (e.g., intravenous, nasal), and durability of effect (e.g., freedom from pain within 2 hours, often satisfied with speed of pain relief) subcategorized as never, rarely, some of the time, most of the time, or all of the time.

Endpoints marked with “*” will be also be summarized by subgroup level and overall for treated subjects by all subgroups of interest defined in Section 4.2.6. Endpoints marked with “#” will also be summarized by enrollment group and overall for screened subjects who were not treated.

The number and percentage of subjects in all subgroups specified in Section 4.2.6 will be tabulated for treated subjects by enrollment group and overall.

These data will also be provided in by-subject listings.

For screened subjects who were not enrolled, baseline is defined as the last non-missing value available. For enrolled subjects who were not treated, baseline is defined as the last non-missing value on or before the IWRS enrollment date/time. For treated subjects, baseline is defined as

the last non-missing value on or before the study drug first dose date/time (i.e., in the pre-treatment analysis period; see Sections 5.3 and 5.4).

Age (years) at informed consent is calculated as: (informed consent date - birth date + 1) / 365.25.

For migraine history, time since last migraine (days) is calculated as informed consent date – imputed last migraine date for subjects with imputed last migraine date up to 1 year before informed consent date. Last migraine dates will be imputed for partial and missing dates using the same methodology as for imputation of AE start dates, but using the informed consent date as the surrogate date. Refer to the BHV3000 Core SAP for AE start date imputation.

For each subject, multiple medical histories of the same SOC or PT will be counted only once within each SOC and PT. Medical histories will be presented in descending order of overall frequency within SOC and PT.

4.6 Safety, Tolerability and Other Evaluations

Unless otherwise noted, all primary, secondary and exploratory analyses will be conducted using all treated subjects. All data will also be included in by-subject listings that will include enrollment group and time point (as applicable). The terms “on-treatment” and “follow-up” will apply to the on-treatment and follow-up safety analysis periods, respectively (see Section 5.4) unless specified otherwise.

Outcomes research (non-safety) questionnaires and rating scales are MSQoL, MIDAS, CGI-C, PoM, and SM (see Section 2.3.3). MSQoL, MIDAS, and CGI-C will be summarized as continuous parameters at baseline and each scheduled visit over time. Post-baseline measurements will be slotted into analysis visit windows in the post-enrollment and follow-up analysis periods (see Section 5.4). If a subject has multiple values in an analysis visit window, then the non-missing value closest to the target date for the visit will be used; in the case of a tie, the latest value collected will be used. See Sections 4.5, 5.4 and 5.5 for definitions of baseline, analysis periods, and analysis visit windows, respectively.

4.6.1 Primary Safety Endpoints

The following primary endpoints to examine safety and tolerability are summarized by enrollment group and overall: frequency and severity of AEs occurring in $\geq 5\%$ of treated subjects, SAEs, AEs leading to study drug discontinuation, and clinically significant laboratory abnormalities.

On-treatment AEs as described above will be shown in separate tables by SOC and PT for each endpoint (AEs occurring in $\geq 5\%$ of subjects in any enrollment group by severity [mild, moderate, severe, moderate or severe, not reported, total], SAEs, AEs leading to study drug discontinuation). The 5% cut applies to the percentage of subjects with a PT in any enrollment group, regardless of severity. See Section 4.8.2 for additional details about AEs, and a comprehensive list of AE tables. Refer to the BHV3000 Core SAP for rounding rules.

4.6.2 Secondary Safety Endpoints

The following secondary endpoints will be summarized by enrollment group and overall: frequency of on-treatment elevations of AST or ALT $> 3 \times$ ULN concurrent with TBL $> 2 \times$ ULN; frequency and severity of on-treatment hepatic-related AEs; and frequency of on-treatment hepatic-related AEs leading to study drug discontinuation.

AST or ALT $> 3 \times$ ULN concurrent with TBL $> 2 \times$ ULN is defined as elevations on the same collection date, and will be summarized as the number and percentage of subjects experiencing these elevations concurrently on treatment and during follow-up. This will include two-sided Agresti-Coull 95% CIs for each percentage. These will be summarized together in the same table as other LFT elevation endpoints (see Section 4.6.3.1).

Refer to the BHV3000 Core SAP for hepatic-related AEs.

See also Section 4.8.2 for additional details about AEs, and a comprehensive list of AE tabulations.

4.6.3 Exploratory Safety and Other Endpoints

4.6.3.1 LFT Elevations

The number and percentage of subjects with LFT elevations will be summarized separately for the following populations and safety analysis periods:

- Screened subjects during pre-treatment by enrollment group, and overall
- Treated subjects during pre-treatment by enrollment group and overall
- Treated subjects on-treatment by enrollment group and overall
- Treated subjects on-treatment by subgroup level and overall for all subgroups of interest specified in Section 4.2.6
- Treated subjects on-treatment by enrollment group and overall for subjects who did not participate in previous Studies BHV3000-301/302/303
- Follow-up subjects during follow-up by enrollment group and overall.

LFT elevations include the following endpoints:

- Cumulative elevations:
 - ALT $> 1 \times, > 3 \times, > 5 \times, > 10 \times$, and $> 20 \times$ ULN
 - AST $> 1 \times, > 3 \times, > 5 \times, > 10 \times$, and $> 20 \times$ ULN
 - ALT or AST $> 1 \times, > 3 \times, > 5 \times, > 10 \times$, and $> 20 \times$ ULN
 - TBL $> 1 \times, 1.5 \times$, and $> 2 \times$ ULN
 - Alkaline phosphatase (ALP) $> 1 \times, > 1.5 \times$, and $> 2 \times$ ULN

- Mutually exclusive elevations:
 - ALT > ULN to $\leq 3 \times$ ULN, $> 3 \times$ ULN to $\leq 5 \times$ ULN, $> 5 \times$ ULN to $\leq 10 \times$ ULN, $> 10 \times$ ULN to $\leq 20 \times$ ULN, and $> 20 \times$ ULN
 - AST > ULN to $\leq 3 \times$ ULN, $> 3 \times$ ULN to $\leq 5 \times$ ULN, $> 5 \times$ ULN to $\leq 10 \times$ ULN, $> 10 \times$ ULN to $\leq 20 \times$ ULN, and $> 20 \times$ ULN
 - ALT or AST > ULN to $\leq 3 \times$ ULN, $> 3 \times$ ULN to $\leq 5 \times$ ULN, $> 5 \times$ ULN to $\leq 10 \times$ ULN, $> 10 \times$ ULN to $\leq 20 \times$ ULN, and $> 20 \times$ ULN
- Composite elevations:
 - ALT or AST $> 3 \times$ ULN and TBL $> 1.5 \times$ ULN
 - ALT or AST $> 3 \times$ ULN and TBL $> 2 \times$ ULN
 - ALT or ALT $> 3 \times$ ULN concurrent with TBL $> 2 \times$ ULN with Agresti-Coull 95% CIs (see Section 4.6.2)
 - ALT or ALT $> 3 \times$ ULN concurrent with TBL $> 2 \times$ ULN and ALP $\leq 2 \times$ ULN with Agresti-Coull 95% CIs (see Section 4.6.2)
 - ALT or AST $> 3 \times$ ULN concurrent with AEs of interest (nausea, vomiting, anorexia, abdominal pain, fatigue; see Section 4.6.3.2).

Exposure-adjusted on-treatment cumulative LFT elevations will also be summarized for treated subjects with the number and percentage of subjects with LFT elevations, along with patient-years and exposure-adjusted rates based on exposure up to time of first LFT elevation (see Section 4.8.2).

By-subject longitudinal LFT plots will display all normalized results (i.e., LFT ratio of value to ULN) regardless of study period for AST, ALT, ALP and TBL on the y-axis versus study week of laboratory result on the x-axis for treated subjects with any of the following LFT elevations during a safety analysis period (pre-treatment, on-treatment, follow-up): ALT $> 3 \times$ ULN; AST $> 3 \times$ ULN; TBL $> 2 \times$ ULN; ALP $> 2 \times$ ULN. Study week is defined as study day/7 (see Section 5.5). Each figure will also display treated migraine onsets, start of the on-treatment safety analysis period, and start of the follow-up safety analysis period.

Additionally, an evaluation of Drug-Induced Serious Hepatotoxicity (eDISH) scatter plot will display the maximum TBL ratio of value to ULN on the y-axis versus the maximum ALT ratio of value to ULN on the x-axis, where the maxima will be in the same safety analysis period but not necessarily concurrent. Both axes will be on the \log_{10} scale. Ratios $< 0.1 \times$ ULN will be set to 0.1. Sample sizes in the legend will represent subjects with paired ratios. A horizontal reference line will be placed at $2 \times$ ULN, and a vertical reference line will be placed at $3 \times$ ULN. The lower left quadrant will be labeled “Normal Range”, the upper left quadrant will be labeled “Hyperbilirubinemia”, the lower right quadrant will be labeled “Temple’s Corollary”, and the upper right quadrant will be labeled “Possible Hy’s Law Range.” The following eDISH scatter plots will be produced for treated subjects: (1) on-treatment by enrollment group; (2) on-treatment by average rimegepant exposure; (3) on-treatment by average rimegepant exposure for the EOD+PRN dosing group; (4) on-treatment by enrollment group for treated subjects who

took ≥ 14 tablets per 4 weeks for ≥ 12 weeks; (5) by safety analysis period (pre-treatment, on-treatment, follow-up) across enrollment groups pooled; (6) on-treatment by enrollment group for treated subjects who took ≥ 20 tablets per 4 weeks for ≥ 4 weeks; (7) on-treatment by enrollment group for treated subjects with near-daily dosing.

Rates of multiple on-treatment, cumulative and mutually exclusive LFT elevations will be summarized using descriptive statistics for treated subjects (1) enrollment group and overall, and (2) subgroup level and overall for key extrinsic exposure factors. For each subject and LFT elevation endpoint, the rate is defined as total number of elevations/total number of non-missing values during the on-treatment period. Multiple values on the same collection date will be counted only once.

The number and percentage of subjects with time to first on-treatment LFT elevations ($ALT > 3 \times ULN$; $AST > 3 \times ULN$; ALT or $AST > 3 \times ULN$) will be presented by enrollment group and overall for treated subjects with on-treatment LFT elevations in the following categories: ≤ 2 , > 2 to ≤ 4 , > 4 to ≤ 8 , ..., > 48 to ≤ 52 , > 52 weeks. Time to elevation is calculated as $(LFT \text{ collection date} - \text{study drug first dose} + 1)/7$.

In all of these analyses described in this section, subjects must have non-missing LFT data (i.e., ALT , AST , TBL , or ALP) in the safety analysis period to be included.

4.6.3.2 *ALT or AST > 3 x Upper Limit of Normal (ULN) Concurrent with Nausea, Vomiting, Anorexia, Abdominal Pain or Fatigue*

AST or $ALT > 3 \times ULN$ elevations that are concurrent with nausea, vomiting, anorexia, abdominal pain or fatigue will be summarized, as the number and percentage of subjects experiencing this concurrently, in the same table as other LFT elevation endpoints described in Section 4.6.3.1. For a given safety analysis period (pre-treatment, on-treatment, follow-up), an LFT elevation is concurrent with an AE of interest if the imputed AE start date is $+\/- 7$ days inclusive of the LFT collection date; both the LFT collection date and the imputed AE start date must also be in the safety analysis period. Refer to the BHV3000 Core SAP for AE start date imputation. The following will be used to identify the AEs of interest: nausea, vomiting, anorexia, fatigue, and those containing “abdominal pain”.

4.6.3.3 *LFT Elevations by Gender, Age, and Rimegepant Exposure*

See Section 4.6.3.1.

4.6.3.4 *Secondary Safety Endpoints by Rimegepant Exposure*

Secondary safety endpoints as described in Section 4.6.2 will be assessed by several study drug exposure groups for treated subjects. The number and percentage of subjects with hepatic-related SAEs by SOC, PT and severity, hepatic-related AEs leading to study drug discontinuation by SOC and PT, and concurrent elevations of AST or $ALT > 3 \times ULN$ with $TBL > 2 \times ULN$ will be shown by subgroup level and overall for extrinsic exposure subgroups (see Section 4.6.2). Only treatment-emergent AEs and on-treatment laboratory test values will be included.

4.6.3.5 *Number and Severity of Migraine Days per Month*

Subjects are instructed to report migraine status (yes, no, unable to recall) and severity (mild, moderate, severe, unable to recall) in their diaries every day.

Migraine days per month will be assessed as “migraine days per 4 weeks” to correspond with the 4-week visit schedule. Analyses will be based on the OP and LTT analysis periods for evaluable treated subjects, i.e., treated subjects who had ≥ 14 days of data (not necessarily consecutive) in both the OP analysis period and at least one 4-week interval in the LTT analysis period.

- A day of data is defined as an eDiary record with complete date and {yes or no} response to having a migraine. If a subject has multiple responses or migraine severities on the same date, then the most severe migraine last sequenced chosen. Only days of data are included in analyses.
- A migraine day is defined as a day of data with a “yes” response to having a migraine.
- 4-week (28-day) intervals are defined from LTT start as: interval 1 (≤ 4 weeks; LTT study days 1 to 28), interval 2 (> 4 to ≤ 8 weeks; LTT study days 29 to 56), ..., interval 13 (> 48 to ≤ 52 weeks; LTT study days to 336 to 364), interval 14 (> 52 to ≤ 56 weeks; LTT study days to 365 to 392). See Section 5.5 for the definition of LTT study days.

Thus, the total numbers of days of data and migraine days are calculated for the OP analysis period and for each 4-week interval in the LTT analysis period.

OP records will come from the screening epoch, whereas LTT records will be come from the treatment epoch.

Tables will present results by enrollment group and overall separately for (1) evaluable treated subjects, (2) evaluable treated subjects with ≥ 14 migraine days per 4 weeks in the OP, (3) evaluable treated subjects with ≥ 20 migraine days per 4 weeks in the OP, and (4) evaluable treated subjects taking concomitant prophylactic migraine medication (see Section 4.9). In addition, tables will present results by average rimegepant exposure and overall for evaluable EOD+PRN treated subjects (see Section 4.2.6).

The number of migraine days per 4 weeks in the LTT period will be examined relative to the number of migraine days per 4 weeks in the OP by severity (total [mild, moderate, severe, unable to recall, not reported]; moderate or severe). The following tables will be produced:

- Values and changes (both absolute and percent) from the OP in the number of migraine days per 4 weeks in 4-week intervals during LTT and overall LTT average will be summarized using descriptive statistics by severity (including two-sided 95% normal CIs for mean change). The number of migraine days per 4 weeks will be prorated to 28 days and derived as follows:
 - OP: $28 * (\text{total number of migraine days in the OP analysis period}) / (\text{total number of data days in the OP analysis period})$.

- 4-week interval during LTT: $28^*(\text{total number of migraine days in the interval})/(\text{total number of data days in the interval})$. In addition, subjects must have ≥ 14 days of data (not necessarily consecutive) in an interval to be evaluable for that interval.
- Overall LTT average: $28^*(\text{total number of migraine days in the LTT analysis period}) / (\text{total number of data days in the LTT analysis period})$.
- Number and percentage of subjects with $< 1, \geq 1, \geq 2, \geq 3, \geq 4$ and ≥ 5 decrease from the OP and $\geq 20\%, \geq 25\%, \geq 30\%, \geq 35\%, \geq 40\%, \geq 45\%$, and $\geq 50\%$ decrease from the OP in the number of migraine days per 4 weeks in 4-week intervals during LTT and overall LTT average by severity.

A scatter plot by enrollment group will display the decrease in the number of migraine days per 4 weeks in the overall LTT average from the OP (y-axis) versus number of migraines per 4 weeks in the OP (x-axis). Another scatter plot by enrollment group will display the percent decrease in the number of migraine days per 4 weeks in the overall LTT average from the OP (y-axis) versus number of migraine days per 4 weeks in the OP (x-axis). Plots will include a horizontal reference line at 0. These scatter plots will also be produced by average rimegepant exposure for evaluable EOD+PRN treated subjects (see Section 4.2.6).

In the percent change/decrease analyses, subjects must also have ≥ 1 total number of migraine days during the OP to be included.

A by-subject listing will present migraine attacks and severity for screened subjects. Another by-subject listing will present the number of migraine days per 4 weeks during the OP, overall LTT average, and in 4-week intervals during the LTT for treated subjects.

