#### 3 STUDY ENDPOINTS

#### 3.1 Primary

The frequency and severity of adverse events that occur in at least 5% of treated subjects, the frequency of serious adverse events, adverse events leading to discontinuation and clinically significant laboratory abnormalities during the treatment period will be assessed. The frequency of AEs and SAEs are determined from case report forms, and are tabulated based on the number of unique subjects. The frequency of clinically significant laboratory abnormalities are determined from laboratory data, and are also tabulated based on the number unique subjects.

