- TEAEs occurring in $\geq 2\%$ of subjects in any enrollment group after rounding. Percentages will be displayed rounded to integers, and AEs will be displayed in alphabetical order by SOC and PT.
- AEs occurring in $\geq 2\%$ of subjects in any enrollment group or subgroup level[^]
- AEs occurring in $\geq 5\%$ of subjects in any enrollment group by severity (primary safety endpoint, see Section 4.6.1)
- AEs occurring in $\geq 10\%$ of subjects in any enrollment group
- Exposure-adjusted AEs
- AEs related to study drug by severity*
- AEs related to study drug occurring in $\geq 2\%$ of subjects in any enrollment group or subgroup level[^]
- SAEs (primary safety endpoint, see Section 4.6.1)*
- Exposure-adjusted SAEs
- AEs leading to study drug discontinuation (primary safety endpoint, see Section 4.6.1)*
- Hepatic-related AEs by severity (secondary safety endpoint, see Section 4.6.2)[#]
- Hepatic-related SAEs[#]
- Hepatic-related AEs leading to study drug discontinuation (secondary safety endpoint, see Section 4.6.2)[#]
- Additional AEs of special interest: potential drug abuse[^]; CV; suicidality. Potential drug abuse AEs will be displayed in alphabetical order by severity and PT without SOC.

Endpoints marked with “*” will also be summarized by subgroup level and overall for all subgroups of interest specified in Section 4.2.6. Endpoints marked with “#” will also be summarized by subgroup level and overall only for extrinsic exposure factors (see Section 4.2.6). Endpoints marked with “^” will also be summarized by subgroup level and overall only for key extrinsic exposure factors (see Section 4.2.6).

Refer to the BHV3000 Core SAP for exposure-adjusted AEs. Calculations for on-treatment exposure-adjusted AEs will set reference start date to the study drug first dose date, reference end date to the study drug end dose date, and reference last date to the study drug last dose date + 7 days.

Follow-up AEs

Follow-up AEs will be summarized by SOC and PT for follow-up subjects by enrollment group and overall for the following endpoints:

- AEs by severity
- SAEs.

AEs in All Safety Analysis Periods Combined

AEs in all safety analysis periods combined (i.e., pre-treatment, on-treatment, and follow-up) will be summarized by SOC and PT for treated subjects by enrollment group and overall for the following endpoints:

- AEs leading to study drug discontinuation (primary safety endpoint, see Section 4.6.1)

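### Two SAP specification errors to correct before programming: the concurrent liver rows omit AST, and the hepatic AE tables by exposure are given two different AE sets

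*SAP*

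**What the plan says.** **Liver endpoint.** SAP 4.6.2 states that "AST or ALT $> 3 \times$ ULN concurrent with TBL $> 2 \times$ ULN is defined as elevations on the same collection date", and places the result in the LFT table: "These will be summarized together in the same table as other LFT elevation endpoints (see Section 4.6.3.1". SAP Table 2, SAP 4.6.3.4 and Protocol 9.3.2 also include both enzymes. Among the composite elevations in SAP 4.6.3.1, the row for this endpoint reads "ALT or ALT $> 3 \times$ ULN concurrent with TBL $> 2 \times$ ULN with Agresti-Coull 95% CIs". The next row, which adds an alkaline phosphatase condition, has the same doubled ALT. Both rows refer back to 4.6.2.

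**Hepatic AEs by exposure.** SAP 4.6.3.4 covers hepatic-related SAEs, hepatic-related AEs leading to discontinuation and the concurrent LFT elevation, broken down by exposure subgroup. It says: "Only treatment-emergent AEs and on-treatment laboratory test values will be included". SAP Table 3 defines the corresponding exploratory estimand on treatment. In SAP 4.8.2, under the on-treatment heading, hepatic-related SAEs and "Hepatic-related AEs leading to study drug discontinuation (secondary safety endpoint, see Section 4.6.2") both carry the mark that calls for a further breakdown by extrinsic exposure factor.

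**Common AEs.** Protocol 3.1 gives the primary endpoint as "The frequency and severity of adverse events that occur in at least 5% of treated subjects". SAP Table 1 and the opening sentence of SAP 4.6.1 use the same denominator. The next paragraph of 4.6.1 gives the working rule: "The 5% cut applies to the percentage of subjects with a PT in any enrollment group, regardless of severity". SAP 4.8.2 lists its primary 5% table on that rule.

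**The concern.** Change in liver function tests is the main AE of interest that the protocol names (Protocol 1.3.4), and the concurrent elevation is the secondary laboratory endpoint. Few or no cases may occur, so a row that overlooks one qualifying subject can alter the reported result.

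The hepatic AE tables by exposure raise a different question. Two sections specify the same output with different AE sets, and a programmer cannot satisfy both. If the sets differ for even one subject, a table built from 4.6.3.4 will not match one built from 4.8.2, and the report will have to explain why.

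**Working it through.** **The plan's own figure.** SAP 4.1 gives a one-sided 95% upper bound with zero events of about 0.0015 for 2000 subjects and 0.00375 for 800. The rule of three gives 3/2000 = 0.0015 and 3/800 = 0.00375. The exact form, 1 - 0.05^(1/n), gives 0.001497 and 0.003738. Both figures reproduce and neither is in dispute. They are not the interval for the liver endpoint, which SAP 4.6.2 sets as two-sided Agresti-Coull.

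**1. The ALT/AST rows**

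- Direction: every subject who meets the condition through ALT also meets it through ALT or AST, so the literal count can only be equal or lower.
- Second specification: 4.6.3.1 requires its LFT table for all subgroups in 4.2.6, which include exposure. 4.6.3.4 requires the same concurrent endpoint by exposure with AST or ALT. One result therefore has two written definitions.
- Illustration, assuming one AST-only case among 2000 treated subjects (the planned total). The Agresti-Coull upper limit is p + z x sqrt(p(1 - p)/m), with z = 1.96, m = n + z² = 2003.84 and p = (x + z²/2)/m.
  - x = 1: p = 2.9207/2003.84 = 0.0014576. Standard error 0.0008522. Upper limit 0.0014576 + 1.96 x 0.0008522 = 0.00313, or 31.3 per 10,000.
  - x = 0: p = 1.9207/2003.84 = 0.0009585. Upper limit 0.00231, or 23.1 per 10,000.

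The documents give no rate of AST-only cases, so this is the effect of one lost case and not a forecast.

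**2. Treatment-emergent against on-treatment**

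| Place in SAP | Output | AE set |
|---|---|---|
| Table 3 | hepatic SAEs and discontinuations by exposure | on treatment |
| 4.8.2, marked rows | the same, by extrinsic exposure factor | on-treatment |
| 4.6.3.4 | the same, by extrinsic exposure subgroup | treatment-emergent only |

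The SAP does not use the two terms as synonyms: the AE listing in 4.8.2 flags each separately, and each has its own overview table. The revision history records that version 2.0 changed treatment-emergent to on-treatment in 2.3, 4.6.1, 4.6.2 and many places in 4.8.2, and logs no such change for 4.6.3.4. That log is not itself evidence of an error, but it suggests that the phrase was left behind. No count can be computed, because the definition of a treatment-emergent AE is in the BHV3000 Core SAP, which was not available.

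4.6.3.4 also cites 4.6.2 for the exposure subgroups. They are defined in 4.2.6.

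**3. The 5% cut** (planned groups of 1200, 600 and 200)

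- Pooled rule: 0.05 x 2000 = 100 subjects.
- Any-group rule: 60 of 1200, 30 of 600 or 10 of 200, which is 3.0%, 1.5% or 0.5% of all treated subjects.
- Containment: with no group at 5%, at most 59 + 29 + 9 = 97 subjects can have the term, which is below 100. Every term that passes the pooled rule therefore also passes the any-group rule.

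The rule decides which preferred terms are shown. It changes no count.

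**The case against.** The doubled ALT is an obvious slip. As an instruction it is redundant, both rows point to the correct definition, and a careful programmer would query it. Even on a literal reading, an AST-only case would appear in the neighbouring non-concurrent row for ALT or AST with bilirubin above 2 x ULN, in a by-subject plot triggered by AST above 3 x ULN, and in the LFT listing. All of this stands, and it limits the harm. The row at fault is nevertheless the one that carries the secondary endpoint and its interval.

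The AE-set conflict touches only an exploratory breakdown. The primary AE tables and the main hepatic tables are on-treatment throughout, and the treatment-emergent tables in 4.8.2 are labelled additions. This also stands. It does not settle which set the by-exposure tables should use.

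A reader might infer that the primary and secondary endpoints rest on rival rules, so that their tables are bound to disagree. The documents do not support that. The ALT slip bites only if followed literally, the AE-set difference is exploratory and of unknown size, and the 5% cut has one explicit operating rule and one primary table.

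A reader might also infer that SAP Section 6 is wrong to report no changes from the protocol. That cannot be shown. The SAP is based on protocol Version 6, which added a 12-week cohort taking CGRP biologics. The protocol supplied has no such cohort, so it is not that version.

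**Conclusion.** The point holds as two specification errors in the current SAP. The first is a typing error in the two concurrent LFT rows of 4.6.3.1. Its effect is nil if the programmer follows 4.6.2. If the rows are followed literally, AST-only cases are lost from the secondary endpoint row, and each lost case matters when few or none are expected. The 31.3 and 23.1 per 10,000 assume 2000 treated subjects and one such case.

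The second is a real conflict of rules between 4.6.3.4 and both Table 3 and 4.8.2, confined to exploratory tables. Counts may differ; whether they do, and by how much, depends on the Core SAP.

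The 5% wording is a matter of alignment inside the SAP only. The any-group list contains the pooled list, and the count for each term is the same under either rule.

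**What to change.** - In 4.6.3.1, write ALT or AST in both concurrent rows, including the one with the alkaline phosphatase condition.
- In 4.6.3.4, replace treatment-emergent by on-treatment, to agree with Table 3 and 4.8.2, and cite 4.2.6 for the exposure subgroups.
- As minor alignment, bring Table 1 and the first sentence of 4.6.1 into line with the any-enrollment-group rule that the SAP already applies.

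The cost is a wording revision to the SAP. No data collection, sample size or further analysis is involved, and if done before programming no output has to be rerun.
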